8.4.3.3 Exploratory Effectiveness Analysis

Supporting measures:

Frequency and type of supporting measures (e.g. PSP, psycho-oncological support, nutritional advice etc.) will be summarised for each visit by descriptive statistics providing counts and percentages of each category for categorical nominal variables with 95% CIs.

Exploratory correlation analyses:

Details of exploratory correlation analyses assessing the following correlations will be provided in the SAP. The exploratory analyses will mainly focus on the description of:

- DCR and ORR depending on the number and grade of treatment-related AEs (ADRs).
- DCR and ORR depending on the implementation of dose reductions of cabozantinib.
- The evolution of the hrQoL assessed by EORTC QLQ-C30 and additionally QLQ-GINET 21 for GI-NET participants depending on the occurrence of ADRs and dose reductions.
- The DoT and treatment discontinuation due to AEs in regard to supportive measures the participants received.
- The DoT in regard to dose reduction.
- The DoT in regard to hrQoL.

8.4.4 Safety Analysis

Safety analyses will be performed on the Safety population.

During the Treatment Period (Visit 2 to Visit 9), all treatment-emergent AEs including nonserious AEs and SAEs and SS including pregnancy will be collected.

Analysis of AEs

A treatment-emergent AE is defined as any AE that occurs after the first dose of study treatment if:

- It was not present prior to receiving the first dose of study treatment; or
- It was present prior to receiving the first dose of study treatment but the intensity increased during the active phase of the study.

The focus of analysis of this study will be the duration of the Treatment Period, i.e. up to 30 days after the permanent discontinuation of cabozantinib.

An overall summary table of all AEs (including fatal events) will be presented with the number and proportion of participants and the number of events, including frequency of SAEs, drug-related AEs and drug-related SAEs. Summary incidence tables of all AEs, SAEs and AEs by relationship and intensity/grade to study drug will be provided, classified by primary System Organ Class (SOC) and Preferred Term (PT).

All AEs will be coded according to the Medical Dictionary for Regulatory Activities (MedDRA) and will be classified by MedDRA PT and SOC.

All safety data will be included in the participant data listings, such as listings of all AEs, SAEs, AEs leading to study drug withdrawal, AEs leading to dose reduction or interruption and listings of deaths.

Analysis of "Special Situation"

SSs will be listed separately, and summary incidence tables will be provided. The AEs associated with SSs will be described.

PAGE 37/52

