- ¹ Supporting measures include the recording of participation in a PSP, use of psycho-oncological support or nutritional advice.
- ^j In particular, start of new treatment, type of treatment, treatment line and DCR within 12 weeks. For the determination of the DCR after therapy switch, the last TA prior to therapy switch serves as the baseline TA.
- ^k Only AEs related to cabozantinib as assessed by investigator.

PAGE 23/52

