6.1.1 Primary Effectiveness Endpoint

Disease control rate (DCR):

DCR is defined as proportion of participants who within 6 months achieve complete response (CR), partial response (PR) or stable disease (SD) determined based on radiographic assessments between the date of the first dose of cabozantinib until the date of progressive disease (PD) or date of subsequent therapy.

Disease response definitions:		
CR	Complete response	Complete resolution of all visible disease.
PR	Partial response	Partial reduction in size of visible disease in some or all areas without any areas of increase in visible disease. Captures a decrease in disease volume even though disease is still present.
SD	Stable disease	No change in overall size of visible disease. Also includes cases where some lesions increased in size and some lesions decreased in size.
PD	Progressive disease	Increase in visible disease and/or presence of any new lesions. Includes cases where the clinician indicates PD or progression of disease as the overall assessment.

Table 6-1 Disease response definitions

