6.2.1 Adverse Events and Special Situations

The collection and reporting of AEs and Special Situations (SS) will follow regulations related to non-interventional studies.

The definition of AEs and SAEs can be found in Section 9.1. For the management and reporting of the AEs and SS, please refer to Section 9.

All AEs, whether they are serious/nonserious, related/unrelated, and all SS should be collected throughout the observation period of cabozantinib treatment. After cabozantinib treatment has ended, only serious/nonserious AEs that are related to cabozantinib, as assessed by the investigator, that occur during the 3-month follow-up period are collected. All AEs will be assessed according to incidence, intensity/grade, causality, outcome, action taken and seriousness.

The investigator and any qualified designees are responsible for detecting, documenting, and recording events that meet the definition of an AE or SAE and remain responsible for following up any AEs or SAEs.

PAGE 31/52

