9.1.4 Adverse Events of Special Interest

Not applicable

9.2 Time Period and Frequency for Collecting and Reporting AE, SS and SAE Information

For the definition of the AEs and SS, please refer to Section 9.1.

During the Treatment Period, (i.e. from Day 1 until 30 days after discontinuation of cabozantinib treatment or EoS), all AEs including nonserious AEs and SAEs, and SS will be collected. During the Post-treatment Follow-up Period (i.e. from 30 days after discontinuation of cabozantinib treatment until the EoS), only new AEs assessed as related to cabozantinib that start during this period will be collected. Incidence of pregnancy will be collected until 5 months after EoS. If possible, pregnancy should be followed up until the outcome is known. Any further follow-up information on ongoing AEs (until resolution or stabilisation) and SS including pregnancy that occurred during the Treatment Period will be collected.

PAGE 42/52

From this point onwards, the term 'Safety Report' will collectively refer to all reports of non-serious related AEs, SAEs, fatal outcomes and SS.

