9.2.1 Collection of the AEs/SAEs/SS in the eCRF

The collection and reporting of AEs will follow regulations related to non-interventional studies.

All AEs, whether they are serious/nonserious, related/unrelated, and all SS should be collected in the eCRF during the course of the study. Adverse events will be assessed according to incidence, intensity/grade, causality, outcome, action taken and seriousness.

All AEs will be collected in the eCRF from the first intake of cabozantinib until study completion, i.e. EoS or the EoS/follow-up visit, as specified in Table 4-1.

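### The 30-day all-cause AE window has no break at the start of the next line, and the protocol's rules on which AEs are collected after the last dose contradict each other

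*Protocol*

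**What the plan says.** **Analysis window.** Section 8.4.4 puts the focus of the AE analysis on "the duration of the Treatment Period, i.e. up to 30 days after the permanent discontinuation of cabozantinib". Its definition of a treatment-emergent AE has a start (first dose) but no end. It plans incidence tables by SOC and PT for all AEs and for SAEs, and by relationship and grade.

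**Collection after the last dose.** Four places set a rule:

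- Section 9.2 collects AEs of any causality in a Treatment Period running "from Day 1 until 30 days after discontinuation of cabozantinib treatment or EoS". After that, "only new AEs assessed as related to cabozantinib that start during this period will be collected".
- Section 6.2.1: "After cabozantinib treatment has ended, only serious/nonserious AEs that are related to cabozantinib, as assessed by the investigator" are collected during the 3-month follow-up. It has no 30-day tail.
- Table 4-1 footnote k, on the follow-up visit: "Only AEs related to cabozantinib as assessed by investigator". Footnote f makes this the only visit required for participants who stop and switch.
- Section 9.2.1: "All AEs will be collected in the eCRF from the first intake of cabozantinib until study completion", with completion defined as EoS or the EoS/follow-up visit.

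**Effectiveness.** Section 6.1.1 counts disease control only "until the date of progressive disease (PD) or date of subsequent therapy", and Section 6.1.2 cuts ORR at the same point.

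**Next-line date.** Section 4.5 makes the start date of the new treatment minimum required information at follow-up and allows it to be partial.

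**The concern.** The protocol treats the next line as the end of what can be credited to cabozantinib for benefit, but not for harm. A participant may stop cabozantinib and start another agent some days later. An AE of that agent with onset inside the 30 days then meets the treatment-emergent definition and falls in the analysis window. Causality is assessed against cabozantinib only (Section 9.3), so the all-cause tables contain nothing that sets such an event apart.

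The synopsis lists the incidence of all AEs and of all serious AEs, overall and by grade, as a secondary endpoint. The study has one arm, so no comparator would show that part of a preferred-term count came from the next line. In addition, sites following different sections would collect different events over the same 30 days, and the reported incidence would mix the two practices.

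**Working it through.** No figure in the protocol depends on this window, so there is nothing to reproduce. The check compares the texts and then illustrates the size.

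**Step 1. Is there a stop at next-line start?** Sections 8.4.4, 9.2, 9.2.1 and the treatment-emergent definition contain none. The next-line start date is used for DCR, ORR, TTNT and next-line DCR only.

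**Step 2. What happens to an unrelated AE that begins within 30 days of the last dose and after the next line has started?**

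| Rule followed | Collected? | Effect on the Section 8.4.4 all-cause tables |
|---|---|---|
| Section 9.2 | Yes | Counted in the cabozantinib window |
| Section 9.2.1 | Yes | Counted in the cabozantinib window |
| Section 6.2.1 | No | Not counted; the 30-day window is incomplete for unrelated events |
| Table 4-1 footnotes f and k (switchers) | No, if the follow-up visit is the only source | As for Section 6.2.1 |

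Footnote k alone could be reconciled with Section 9.2 if it were meant only for events beyond the 30 days. Section 6.2.1 cannot, because it changes the rule as soon as treatment has ended.

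**Step 3. Is a switch within 30 days plausible?** Section 4.1 places the follow-up visit about 3 months after the switch. Section 4.5 places it about 3 months after discontinuation. The two roughly coincide only when the next line starts soon after the last dose. This suggests early switching but gives no rate.

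**Step 4. Illustration of size.**

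From the protocol: N = 150 (Section 4.1); median duration of treatment in the reference trial 8.3 months for pNET and 5.5 months for epNET (Section 2.3).

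Assumed, not in the protocol: exponential treatment duration; 40–80% of those who stop go on to switch; 25–75% of switchers start within 30 days; 2–10% of these have a next-line SAE inside the window; 40% of participants already have an SAE counted.

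- Off cabozantinib by 15 months, 1 − 0.5^(15/median): pNET 1 − 0.5^(15/8.3) = 0.714; epNET 1 − 0.5^(15/5.5) = 0.849.
- Participants with overlap: low 150 × 0.714 × 0.40 × 0.25 = 10.7; high 150 × 0.849 × 0.80 × 0.75 = 76.4.
- With a next-line SAE in the window: low 10.7 × 0.02 = 0.21; high 76.4 × 0.10 = 7.64.
- Newly counted, after removing those who already have an SAE (× 0.60): low 0.13; high 4.58.
- Added to overall SAE incidence: low 0.13/150 = 0.09 points; high 4.58/150 = 3.06 points.

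The synopsis instead derives expected treatment duration from median PFS (13.8 and 8.4 months). The fractions off treatment are then 1 − 0.5^(15/13.8) = 0.529 and 1 − 0.5^(15/8.4) = 0.710. The low end becomes 150 × 0.529 × 0.40 × 0.25 = 7.9 participants with overlap and 7.9 × 0.02 × 0.60/150 = 0.06 points, still 0.1 when rounded.

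**The case against.** A fixed 30-day all-causality window is an ordinary convention. An all-cause table counts events and does not claim that the drug caused them. Attribution is handled separately: Section 8.4.4 plans drug-related AE and SAE summaries, and Section 9.3 tells investigators to weigh concomitant therapy and other causes. Among the measures that Section 3 singles out for safety (SAEs, drug-related nonserious AEs, drug-related SAEs), only the first is exposed. Section 8.4.4 speaks of a focus of analysis, and Section 8 says that its content may change in the SAP. Cutting at the next line also has a price: it shortens observation most in participants who switch fastest, possibly because of toxicity.

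Much of this stands. The drug-related tables are protected apart from misattribution, and a cut that discarded events would be a poor remedy, so later-onset events should be shown rather than dropped.

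The objection does not remove the point. The protocol writes the window down itself, and all-AE and all-SAE incidence is a stated endpoint. The contradiction over collection must be settled in the protocol before sites enter data, because a later SAP cannot recover events that were never collected.

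**Conclusion.** The point holds conditionally. The window has no separation at next-line start. Depending on the collection rule followed, the all-cause tables either include next-line toxicity or lack unrelated events in the 30-day tail. Neither result is what a reader of Section 8.4.4 would expect.

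Two stronger readings are not supported. A reader might infer that next-line toxicity necessarily enters the tables; Section 6.2.1 and footnotes f and k say otherwise for the very participants who switch. A reader might also count everyone with any next-line AE in the tail and call that the distortion. For example, 121–126 participants stopping by Month 15, 30–70% of them starting the next line within 30 days, and 0.5–2 new AEs per month give 121 × 0.30 × 0.213 ≈ 8 to 126 × 0.70 × 0.568 ≈ 50 participants, using 1 − (1 − e^(−r))/r. Those rates are assumed, and the count is of participants with such an event, not of added incidence: someone with an earlier AE adds nothing to the any-AE figure.

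The size is therefore not known from the documents. For overall SAE incidence it is probably small, about 0.1 to 3.1 percentage points under the inputs above. It falls mainly on preferred terms typical of the next line. The primary endpoint is not touched. The change is worth making because it is cheap, not because the safety conclusions are at serious risk.

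**What to change.** 1. Reconcile Table 4-1 footnote k and Sections 6.2.1, 8.4.4, 9.2 and 9.2.1 so that one rule states which AEs are collected after the last dose and for how long. If unrelated AEs are not to be collected after the last dose, Section 8.4.4 cannot keep a 30-day all-cause window.
2. In Section 8.4.4, tabulate all-causality AEs and SAEs with onset from first dose to the earlier of 30 days after the last cabozantinib dose or the day before the next line starts. Show events with onset after next-line start but within the 30 days in a separate table, so that none is lost.
3. Keep reporting cabozantinib-related AEs up to the follow-up visit, whether or not a next line has started.
4. State a rule for partial next-line start dates, which Section 4.5 allows. One option is to keep the AE in the cabozantinib table unless the available date shows onset after the switch.

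The cost is a consistency amendment to five places, one extra table, and slightly shorter all-cause observation in fast switchers. No new data item is needed, but the partial-date rule is, because the cut works at the level of days.

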8.4.5 Quality of Life Analysis

QLQ-C30 global and subscale scores for each visit at which hrQoL was assessed:

Scoring of EORTC QLQ-C30 global and subscale scores is performed by using the official scoring manual for the questionnaire. Global and subscale scores are analysed by descriptive statistics at each visit with the change from baseline.

QLQ-GINET21 subscale scores for each visit at which hrQoL was assessed:

Scoring of EORTC QLQ-GINET21 global and subscale scores is performed by using the official scoring manual for the questionnaire. Global and subscale scores are analysed by descriptive statistics at each visit with the change from baseline on the subgroup of participants with GI NET.

8.4.6 Medical Resource Utilisation Analysis

Not applicable.

8.5 Subgroup Analyses

Subgroup analyses are only performed if data permit. Subgroups may be merged into larger subgroups if deemed necessary. The following subgroups are defined:

Subgroups NET localisation:

NET-I LungNET (27.3%)
NET-II GI-NET (53.2%)
NET-III pNET (7.3%)
NET-IV Other NET (12.2%)

Estimation for subgroup sample size: The breakdown into subgroups follows the distribution described in the literature for NET [4,6]. Due to the difference in treatment sites for LungNET and other NETs in Germany and Austria the LungNET cohort is estimated to be approx. 20% and the other NETs make up approx. 80% of the sample size. All endpoints will be analysed for the subgroups if participant collective allows it.

Feasibility of subgroup assessment will be completed following the enrolment of all participants in this study. If necessary, these subgroups may be combined to make larger groups.

8.6 Interim Analysis

Three interim analyses are planned:

- 1. Interim analysis 1 (IA1): The first interim analysis is planned to be conducted in Q3 2026, expecting about one third of the target sample size (~ 50 participants) to be enrolled. It will evaluate data from Visit 1 (Baseline) with a focus on participant characteristics and NET medical history.
- 2. Interim analysis 2 (IA2): The second interim analysis is planned to be conducted in Q2 2027, expecting about half of the target sample size (~ 75 participants) to be enrolled. It will evaluate data based on Visit 5 (Month 6) and will focus on effectiveness data, QoL and safety.
- 3. Interim analysis 3 (IA3): The third interim analysis is planned to be conducted in Q1 2028, when full recruitment is expected. Updates on IA2 evaluations will be given as well as analyses on later endpoints and will focus on effectiveness data and post-cabozantinib therapies.

PAGE 38/52

9 MANAGEMENT AND REPORTING OF ADVERSE EVENTS/ADVERSE DRUG REACTIONS AND SPECIAL SITUATIONS

9.1 Definition

9.1.1 Adverse Event

AE Definition

An Adverse Event (AE) is any untoward medical occurrence in a patient/participant, administered a medicinal product (cabozantinib) and which does not necessarily have a causal relationship with this treatment.

NOTE: An AE can therefore be any unfavourable and unintended sign (e.g. an abnormal laboratory finding), symptom, or disease temporally associated with the use of the medicinal product, whether or not related to the medicinal product.

Events Meeting the AE Definition

Any abnormal laboratory test results (haematology, clinical chemistry, or urinalysis) or other safety assessments (e.g. ECG, radiological scans, vital signs measurements), including those that worsen from baseline, considered clinically significant in the medical and scientific judgement of the investigator (i.e. not related to progression of underlying disease).

Exacerbation of a chronic or intermittent pre-existing condition including either an increase in frequency and/or intensity of the condition.

New condition detected or diagnosed after study treatment administration even though it may have been present before the start of the study.

Signs, symptoms, or the clinical sequelae of a suspected drug-drug interaction.

Signs, symptoms, or the clinical sequelae of a suspected overdose of either study treatment or a concomitant medication. Overdose per se will not be reported as an AE/SAE unless it is an intentional overdose taken with possible suicidal/self-harming intent. Such overdoses should be reported regardless of sequelae.

For studies involving marketed products in established indications include:

The signs, symptoms, and/or clinical sequelae resulting from lack of effectiveness will be reported as AE or SAE if they fulfil the definition of an AE or SAE. Also, "lack of effectiveness" or "failure of expected pharmacological action" also constitutes an AE or SAE.

Events NOT Meeting the AE Definition

Any clinically significant abnormal laboratory findings or other abnormal safety assessments which are associated with the underlying disease, unless judged by the investigator to be more severe than expected for the participant's condition.

The disease/disorder being studied or expected progression, signs, or symptoms of the disease/disorder being studied, unless more severe than expected for the participant's condition.

Medical or surgical procedure (e.g. endoscopy, appendectomy): the condition that leads to the procedure is the AE.

PAGE 39/52

Situations in which an untoward medical occurrence did not occur (social and/or convenience admission to a hospital).

Anticipated day-to-day fluctuations of pre-existing disease(s) or condition(s) present or detected at the start of the study that do not worsen.

9.1.2 Serious Adverse Event

If an event is not an AE per definition above, then it cannot be an SAE even if serious conditions are met (e.g. hospitalisation for signs/symptoms of the disease under study, death due to progression of disease).

An SAE is defined as any serious adverse event that, at any dose:

a. Results in death

b. Is life-threatening

The term 'life-threatening' in the definition of 'serious' refers to an event in which the participant was at risk of death at the time of the event. It does not refer to an event, which hypothetically might have caused death, if it were more severe.

c. Requires inpatient hospitalisation or prolongation of existing hospitalisation

In general, hospitalisation signifies that the participant has been admitted (usually involving at least an overnight stay) at the hospital or emergency ward for observation and/or treatment that would not have been appropriate in the physician's office or outpatient setting. Complications that occur during hospitalisation are AEs. If a complication prolongs hospitalisation or fulfils any other serious criteria, the event is serious. When in doubt as to whether "hospitalisation" occurred or was necessary, the AE should be considered serious.

Hospitalisation for elective treatment of a pre-existing condition that did not worsen from baseline is not considered an AE.

d. Results in persistent or significant disability/incapacity

The term disability means a substantial disruption of a person's ability to conduct normal life functions.

This definition is not intended to include experiences of relatively minor medical significance such as uncomplicated headache, nausea, vomiting, diarrhoea, influenza and accidental trauma (e.g. sprained ankle) which may interfere with or prevent everyday life functions but do not constitute a substantial disruption.

e. Is a congenital anomaly/birth defect

f. Other situations:

Medical or scientific judgement should be exercised by the investigator in deciding whether SAE reporting is appropriate in other situations such as significant medical events that may jeopardise the participant or may require medical or surgical intervention to prevent one of the other outcomes listed in the above definition. These events should usually be considered serious.

PAGE 40/52

9.1.3 "Special Situations"

Special situation (SS) is any incidence of drug exposure during pregnancy (i.e. drug exposure to a fetus in utero (whether the fetus is exposed via the mother taking the product or transmission via semen following paternal exposure)) or breastfeeding, overdose, off-label use, medication errors, occupational exposure, abuse, misuse or lack of therapeutic effectiveness whilst using the medicinal product. A SS should be collected by the investigator and reported to Ipsen whether or not these SS are associated with an AE.

